## **12.0 Overall Type-I Error Control**

No hypothesis tests will be conducted for the efficacy analysis.

## 13.0 Version History

**Table 1. SAP Version History Summary**

Version	Date	Summary
1.0	30 Jan 2019	Original version
2.0	07 Feb 2020	The changes made between the second and the first version are: 

• Change of formatting to adhere to a new SAP template

• Small editorial changes for readability and to maintain consistency with the protocol

• An update to include interim analysis.

• Updated the criteria for Liver-Related Elevations to align with Immunology RA project conventions

## **Appendix A. Protocol Deviations**

The number and percentage of subjects who reported at least one of the following protocol deviation categories will be provided.

- Subject entered into the study even though s/he did not satisfy entry criteria.
- Subject developed withdrawal criteria during the study and was not withdrawn.
- Subject received wrong treatment or incorrect dose of study.
- Subject took prohibited concomitant medication.

## Appendix B. Definition of Adverse Events of Special Interest

Adverse Events of Special Interest (AESI) will be identified using the following search criteria:

AESI	Type of MedDRA Query	Broad or Narrow Search	SMQ/CMQ Search Criteria
Serious Infections	CMQ		"Infections" – Subset for SAEs
Opportunistic Infection	CMQ		"Opportunistic Infection"
Possible Malignancy	SMQ	Narrow	"Malignancies"
Malignancy	SMQ		"Malignant tumours"
Non-Melanoma Skin Cancer (NMSC)	SMQ	Broad	Skin Malignant tumours (Broad SMQ) removing Melanoma CMQ
Malignancy excluding NMSC			"Malignant tumours" SMQ removing NMSC output
Lymphoma	SMQ		"Malignant Lymphomas"
Hepatic Disorder (Hepatic Events and Increased Hepatic Transaminases)	SMQ	Narrow	"Drug Related Hepatic Disorders"
Gastrointestinal Perforations	SMQ	Narrow	"Gastrointestinal Perforation"
Anemia	CMQ		"Non-Hemolytic and Non-Aplastic Anemias"
Neutropenia	CMQ		"Hematological Toxicity – Neutropenia"
Lymphopenia	CMQ		"Hematological Toxicity – Lymphopenia (Veliparib Product Specific)"
Herpes Zoster	CMQ		"Herpes Zoster"
Creatine Phosphokinase (CPK) Elevation	PT		Search only for the PT of "Blood creatine phosphokinase increased"
Renal Dysfunction	SMQ	Narrow	"Acute Renal, Failure"
Tuberculosis	CMQ		"Tuberculosis"
Adjudicated Cardiovascular Events	Output from CAC		

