An independent Cardiovascular Adjudication Committee (CAC) will adjudicate blinded cardiac and cerebrovascular events. A CAC charter has been prepared separately from the protocol and defines objective, scope, frequency, and triggers of data reviews.

The clinical trial is to be discontinued or terminated in case of an unacceptable risk, relevant toxicity, or a negative change in the risk/benefit assessment. This might include the occurrence of adverse events

of which character, severity or frequency is new in comparison to the existing risk profile. In addition any data deriving from other clinical trials or toxicological studies which negatively influence the risk/benefit assessment might cause discontinuation or termination of the study.

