If any of the following AEs in [Table 3](#) are reported, the following supplemental report(s) must be completed.

Table 3. Adverse Events Requiring Supplemental Reports

Adverse Event	Supplemental Report
Cardiac events Myocardial infarction or unstable angina Heart failure Cerebral vascular accident and transient ischemic attack Cardiovascular procedures (SAE Supplemental Procedure eCRF)	MACE eCRF
Discontinuation or interruption of study drug due to a hepatic-related AE A hepatic-related SAE ALT/AST > 8 × ULN or ALT/AST > 3 × ULN with a total bilirubin > 2 × ULN	Hepatic AE eCRF
Renal impairment Renal dysfunction Renal failure Serum creatinine > 2.0 mg/dL	Renal eCRF
Herpes zoster infection	Herpes Zoster eCRF
Thrombotic events Non-cardiac, non-CNS embolic or thrombotic event (i.e., deep vein thrombosis or pulmonary embolism)	Embolic and Thrombotic (non-cardiac, non-CNS) eCRF

AE = adverse event; ALT = alanine aminotransferase; AST = aspartate aminotransferase; CNS = central nervous system; eCRF = electronic case report form; MACE = major adverse cardiovascular event; SAE = serious adverse event; ULN = upper limit of normal

If an AE meets any of the following criteria, it is to be reported to AbbVie or Contract Research Organization (as appropriate) as a SAE within 24 hours of the site being made aware of the SAE:

Death of Subject	An event that results in the death of a subject.
Life-Threatening	An event that, in the opinion of the investigator, would have resulted in immediate fatality if medical intervention had not been taken. This does not include an event that would have been fatal if it had occurred in a more severe form.
Hospitalization or Prolongation of Hospitalization	An event that results in an admission to the hospital for any length of time or prolongs the subject's hospital stay. This does not include an emergency room visit or admission to an outpatient facility.
Congenital Anomaly	An anomaly detected at or after birth, or any anomaly that results in fetal loss.

Persistent or Significant Disability/Incapacity

An event that results in a condition that substantially interferes with the activities of daily living of a study subject. Disability is not intended to include experiences of relatively minor medical significance such as headache, nausea, vomiting, diarrhea, influenza, and accidental trauma (e.g., sprained ankle).

Important Medical Event Requiring Medical or Surgical Intervention to Prevent Serious Outcome

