An important medical event that may not be immediately life-threatening or result in death or hospitalization, but based on medical judgment may jeopardize the subject and may require medical or surgical intervention to prevent any of the outcomes listed above (i.e., death of subject, life threatening, hospitalization, prolongation of hospitalization, congenital anomaly, or persistent or significant disability/incapacity). Additionally, any elective or spontaneous abortion or stillbirth is considered an important medical event. Examples of such events include allergic bronchospasm requiring intensive treatment in an emergency room or at home, blood dyscrasias or convulsions that do not result in inpatient hospitalization, or the development of drug dependency or drug abuse.

All AEs reported from the time of study drug administration until 30 days after discontinuation of study drug administration will be collected, whether solicited or spontaneously reported by the subject. In addition, SAEs and protocol-related nonserious AEs will be collected from the time the subject signs the study-specific informed consent.

AbbVie will be responsible for Suspected Unexpected Serious Adverse Reactions (SUSAR) reporting for the Investigational Medicinal Product (IMP) in accordance with global and local requirements.

AEs will be monitored throughout the study to identify any of special interest that may indicate a trend or risk to subjects.

Adverse Events of Special Interest

The following adverse events of special interest (AESI) will be monitored during the study:

- Serious infections
- Opportunistic infections
- Herpes zoster
- Tuberculosis
- Malignancy (all types)
- Gastrointestinal perforations
- Adjudicated cardiovascular events (e.g., major adverse cardiovascular event [MACE])
- Anemia
- Neutropenia

- Lymphopenia
- Increased serum creatinine and renal dysfunction
- Hepatic events and increased hepatic transaminases
- Elevated creatine phosphokinase
- Embolic and thrombotic events (non-cardiac, non-CNS)

Adverse Event Severity and Relationship to Study Drug

The investigator will rate the severity of each AE according to the Rheumatology Common Toxicity Criteria v.2.0. **If no grading criteria are provided for the reported event, then the event should be graded as follows:**

- Mild (Grade 1): Asymptomatic or mild symptoms; clinical or diagnostic observations only; intervention not indicated.

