#### **9.2.6 Adverse Events of Special Interest**

The Adverse Events of Special Interest (AESI) categories will be summarized and presented by "as treated" treatment group and overall using SOC and MedDRA PT. The AESI categories will be identified by the following search criteria per Standard MedDRA Queries (SMQs)/Company MedDRA Queries (CMQs) in [Appendix B](#).

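### SAP Appendix B gives an identification rule for 13 of the protocol's 14 adverse events of special interest and none for embolic and thrombotic events

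*SAP*

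**What the plan says.** Protocol Section 6.1 lists the AESIs to be monitored. Two of them matter here, and they are separate items:

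- "Adjudicated cardiovascular events (e.g., major adverse cardiovascular event [MACE"
- "Embolic and thrombotic events (non-cardiac, non-CNS"

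Table 3 in the same section gives the second its own entry, "Non-cardiac, non-CNS embolic or thrombotic event (i.e., deep vein thrombosis or pulmonary embolism", and its own supplemental form, the "Embolic and Thrombotic (non-cardiac, non-CNS) eCRF". Cardiac and cerebrovascular events go on a different form, the MACE eCRF.

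SAP Section 9.2.6 explains how AESIs are found: "The AESI categories will be identified by the following search criteria per Standard MedDRA Queries", with a pointer to Appendix B. Appendix B opens with "Adverse Events of Special Interest (AESI) will be identified using the following search criteria" and sets out a table of MedDRA queries plus one row fed by the Cardiovascular Adjudication Committee (CAC). No row names embolic or thrombotic events.

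On the CAC, protocol Section 3.3 says it "will adjudicate blinded cardiac and cerebrovascular events", and SAP Section 3.4 describes it in the same way. Protocol Section 3.3 adds: "A CAC charter has been prepared separately from the protocol and defines objective, scope, frequency, and triggers of data reviews". The charter is not among the documents.

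**The concern.** Appendix B decides which events count as AESIs in the analysis. A category named in the protocol but missing from that table drops out of every output built on it, even though sites complete a special form for it. The protocol plainly treats venous thromboembolism as a safety topic: besides the AESI entry and the form, eligibility item 2e excludes subjects with a prior unprovoked DVT or PE.

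What is at stake is the pre-specified grouping. Preferred-term tables show individual terms, but they do not give the number of subjects with any event in the category, and that number is the purpose of an AESI definition. Long-term safety is part of the primary objective.

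Timing adds to this. Protocol Section 7.5 plans an unblinded interim analysis after the Study M16-063 Week 12 lock, and SAP Section 11 describes the sponsor as blinded only until the Study M16-063 lock. A term list written after that point could be written with treatment-level data in view.

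**Working it through.** No power or sample-size figure is involved. The check is a count and a match between two lists.

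**Step 1. Match the lists.**

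| Protocol 6.1 AESI | SAP Appendix B rows |
|---|---|
| Serious infections | 1 |
| Opportunistic infections | 1 |
| Herpes zoster | 1 |
| Tuberculosis | 1 |
| Malignancy | 5 (possible malignancy, malignancy, NMSC, malignancy excluding NMSC, lymphoma) |
| Gastrointestinal perforations | 1 |
| Adjudicated cardiovascular events | 1 (CAC output) |
| Anemia | 1 |
| Neutropenia | 1 |
| Lymphopenia | 1 |
| Creatinine increase and renal dysfunction | 1 (by heading; see the objection) |
| Hepatic events and transaminases | 1 |
| Creatine phosphokinase elevation | 1 |
| Embolic and thrombotic events | **0** |

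- Rows: 17 = 16 MedDRA-based + 1 CAC.
- AESIs reached by the MedDRA-based rows: malignancy uses 5, and the other 16 − 5 = 11 rows serve one AESI each, so 1 + 11 = 12.
- AESIs with a rule: 12 + 1 (CAC) = 13.
- AESIs without a rule: 14 − 13 = 1.

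**Step 2. Look for cover elsewhere in the SAP.**

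- *CAC row.* The stated scope is cardiac and cerebrovascular, while the missing AESI is by name non-cardiac and non-CNS. The protocol lists the two separately and records them on separate forms.
- *Table C-1.* Thrombosis or embolism appears in row B8 and, within injection site reaction, in row D4. Both rows grade severity; neither is a search for AESIs.
- *Section 9.2.2.* Further adverse events may be tabulated on advice from Clinical and Safety. This is discretionary and defines no category.
- *Version history.* Version 2.0 of the SAP postdates the protocol of 06 February 2020, and the history gives no reason for leaving this AESI out.

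**Step 3. Trace the SAP outputs that use the AESI definition.**

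1. Section 9.2.2 overview, AESI line: a subject whose only AESI is a DVT or PE would not be counted.
2. Section 9.2.2, AESI treatment differences with 95% CI: no estimate for this category. This output carries the least weight, because the SAP names no reference arm for any AESI.
3. Section 9.2.6, AESI tables: category absent.
4. Section 9.2.11, listing of subjects with treatment-emergent AESIs: these events absent.
5. Section 11, interim AESI output: category absent.

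That makes five SAP outputs. Separately, protocol Section 7.4 promises percentages and events per 100 patient-years for AESIs. SAP Section 9.2.4 specifies rates for TEAEs without naming AESIs, so this is one protocol commitment and not a sixth SAP output.

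**Step 4. After the fix.** One added row gives 17 + 1 = 18 rows and 14 of 14 AESIs covered.

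**The case against.** The strongest objection is the unseen CAC charter. It defines the committee's scope, and the protocol's cardiovascular AESI gives MACE only as an example, so CAC output might include venous events. That is possible, but nothing in the protocol or SAP supports it, and the stated scope and the separate listing and form point the other way. If it is the intention, the SAP needs to say so.

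The second objection is that little would be hidden, and much of this stands. Events would still appear by preferred term in the Section 9.2.3 tables and, where they qualify, in the serious-event and discontinuation outputs. Table C-1 row B8 puts DVT requiring anticoagulation in Grade 3 and PE in Grade 4, so many would also show among severe events. The DMC reviews unblinded safety data throughout. With 40 to 120 expected completers, individual events could be found by hand. All five affected outputs also trace back to one missing row, so they are not five separate faults. These points limit the harm, but they do not supply the missing definition.

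Three narrower points also stand:

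- Coverage of 13 is by heading. The Renal Dysfunction row is a narrow acute renal failure query, and no row names the creatinine part of that AESI.
- The events are flagged on their own eCRF, so the Section 7.4 summaries could be produced from the data. What is missing is a specification in the SAP. The silence of SAP Section 9.2.4 on rates applies to all 14 AESIs.
- The eCRF is shown only for Study M16-763. The documents do not show that Study M16-063 used it, which matters for the combined-study summaries.

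**Conclusion.** The concern holds. One of 14 protocol AESIs has no identification rule in the SAP, and following the SAP exactly leaves DVT and PE out of five AESI outputs and leaves one protocol commitment unspecified for this category. This rests on the CAC's scope as both documents state it; the charter could not be checked. The consequence is incomplete AESI reporting, not lost data, and no efficacy result is affected. It should be fixed: the omission is clear, it concerns a safety topic the protocol singles out, and the remedy is small.

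**What to change.** Add a row to SAP Appendix B for embolic and thrombotic events (non-cardiac, non-CNS), with a named SMQ or CMQ or a fixed preferred-term list. Cross-check the events it finds against the dedicated eCRF in Study M16-763, and in Study M16-063 if the form was used there. Carry the category into the Section 9.2.2 overview line and differences, the Section 9.2.6 tables, the Section 9.2.11 listing, the Section 11 interim output and the AESI rates promised in protocol Section 7.4. If the sponsor means the CAC row to cover these events, state that in Appendix B instead. The term list is best fixed before treatment-level data are seen.

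The cost is one search row and matching lines in outputs already planned. It needs no new data collection and no protocol amendment.

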2.2 Benefits and Risks to Subjects

Preclinical toxicology studies of ABBV-105 in animals and ex vivo human samples suggest that the potential risks to human subjects of ABBV-105 are anemia, bleeding associated with platelet

dysfunction, and lymphopenia. Reductions in lymphocytes and the known mechanism of action suggest the potential for an increased susceptibility to infection.

ABBV-105 alone and the ABBV-599 combination therapy (with upadacitinib) were well-tolerated with no serious adverse events (SAEs) observed in healthy adult subjects at various doses in 3 Phase 1 studies (Studies M16-356, M16-357, and M16-044). The current study is a continuation of the Phase 2 study of ABBV-105 and ABBV-599 in RA (Study M16-063). Taken together, the safety data from the Phase 1 program and the safe and successful completion of Study M16-063 support further development of ABBV-105 and ABBV-599 in Phase 2 in subjects with RA.

The data from over 4,000 RA patients treated with upadacitinib support an acceptable safety profile and a positive risk-benefit for treatment of adult patients with moderately to severely active RA.

Data from the primary efficacy analyses of the 5 pivotal Phase 3 clinical studies for the upadacitinib RA development program consistently demonstrated the efficacy of upadacitinib 15 mg QD and 30 mg QD, with both doses of upadacitinib meeting all primary and ranked key secondary endpoints across all studies which included all lines of therapy (methotrexate [MTX]-naïve, conventional synthetic disease-modifying antirheumatic drug [csDMARD]/MTX-inadequate responder [IR], and biologic disease-modifying antirheumatic drug [bDMARD]-IR). Upadacitinib 15 mg QD also demonstrated superiority over adalimumab across a broad range of efficacy measures. Overall, the efficacy data in the RA development program provide substantial evidence to support the use of upadacitinib as monotherapy or in combination with MTX and/or csDMARDs for the treatment of adults with moderately to severely active RA.

Serious infections and herpes zoster are identified risks for upadacitinib therapy. The rates of serious infections and herpes zoster for upadacitinib therapy are within the range of other marketed JAK inhibitor products.

In regarding to the potential for malignancy, per upadacitinib Investigator's Brochure version 18.0:

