### **9.2.2 Adverse Event Overview**

The number and percentage of subjects experiencing TEAEs will be summarized by treatment group as specified in Section 6.0 and overall.

An overview of AEs will be presented consisting of the number and percentage of subjects experiencing at least one event for each of the following AE categories:

- All TEAEs
- Treatment-emergent serious adverse events (SAEs)
- Treatment-emergent severe adverse events
- TEAEs reasonably possibly related to study drug
- TEAEs of special interest (AESIs)
- TEAEs leading to discontinuation of study drug

- TEAE leading to death
- All deaths

Additional AEs may be considered for tabulation/summary based on recommendations from Clinical and Safety as deemed appropriate.

For AESIs, the point estimate and 95% CI (using normal approximation) will be provided for the treatment difference in AE percentages.

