### **9.2.11 Listing of Adverse Events**

The following additional summaries of AEs will be prepared.

- Listing of Subjects with Treatment-Emergent AESIs

- Listing of Subjects with Pretreatment SAEs
- Listing of Subjects with Treatment-Emergent SAEs
- Listing of Treatment-Emergent AEs that led to discontinuation of study drug
- Listing of all deaths.

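### The SAP counts the protocol's unrestricted Anemia AESI with one company query whose title leaves out haemolytic and aplastic anaemia, so the AESI count may be incomplete and mislabelled

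*SAP*

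**What the plan says.** Protocol 6.1 introduces its list with "The following adverse events of special interest (AESI) will be monitored during the study". Anemia is one entry, with no qualifier by type or cause. Protocol 2.2 says that preclinical work on ABBV-105 "suggest that the potential risks to human subjects of ABBV-105 are anemia, bleeding associated with platelet" dysfunction, and lymphopenia.

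SAP 9.2.6 says "The AESI categories will be identified by the following search criteria" and points to Appendix B, which opens with "Adverse Events of Special Interest (AESI) will be identified using the following search criteria". The row labelled Anemia holds one entry, the company query "Non-Hemolytic and Non-Aplastic Anemias". The only other blood-count rows are neutropenia and lymphopenia.

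The AESI definition feeds several outputs. SAP 9.2.2 counts AESIs in the overview and adds: "For AESIs, the point estimate and 95% CI (using normal approximation) will be provided for the treatment difference in AE percentages". SAP 9.2.11 plans a "Listing of Subjects with Treatment-Emergent AESIs". SAP 11.0 names AESIs among the key interim safety endpoints. Protocol 7.4 promises AESI percentages and events per 100 patient-years.

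**The concern.** The row label and its search do not have the same scope. A reader of the AESI table sees a line called Anemia and will take it to cover what the protocol calls anemia. If the query does what its title says, two types were never searched for, and the table gives no sign of it. The line could read zero in a group where a haemolytic or aplastic case had occurred.

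An AESI category exists so that a reviewer can read one count without assembling cases from general tables. Anemia is a named potential risk of ABBV-105, and Protocol 2.2 gives no type or mechanism that would justify leaving any type out in advance. Protocol 6.1 also uses blood dyscrasias as an example of an important medical event, so the documents do not treat such events as trivial.

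**Working it through.** The plan gives no figure for this point. The check is a comparison of texts, followed by a trace of the outputs.

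**1. Scope.**

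| Item | Protocol 6.1 | SAP Appendix B |
|---|---|---|
| Label | Anemia, unrestricted | Anemia, unrestricted |
| Search | none given | one company query; title excludes haemolytic and aplastic types |
| Another row for the excluded types | not applicable | none |
| Reason for narrowing | none | none |

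**2. Is the restriction declared?** Other rows show their limits openly. Serious infections are limited in both the label and the search cell, one malignancy row states in its label that non-melanoma skin cancer is removed, and the creatine phosphokinase row says that only one preferred term is searched. The Anemia row puts an unrestricted label over a restricted query title. Two further features suggest that the appendix was not reconciled with the protocol line by line. It has no row for the protocol's embolic and thrombotic AESI, and its lymphopenia query is labelled as specific to a product that is not in this study.

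**3. Where an excluded event would be missing and where it would remain.**

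| Missing from the Anemia AESI count | Still shown |
|---|---|
| Overview and treatment difference (SAP 9.2.2) | All treatment-emergent events by system organ class and preferred term; severe and related tables if they apply (SAP 9.2.3) |
| AESI summary (SAP 9.2.6) | Serious event and discontinuation tables and listings, if they apply (SAP 9.2.5, 9.2.11) |
| AESI listing (SAP 9.2.11) | Haemoglobin change, grading, shift tables and listings of potentially clinically significant values, whatever the cause (SAP 9.3; Table C-1, K1) |
| Interim AESI output (SAP 11.0) | Interim serious events, related events and haematology outputs (SAP 11.0) |
| AESI percentages and rates (Protocol 7.4) | |

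An aplastic case with a separately coded neutropenia or lymphopenia event could enter those AESI rows, but not the Anemia row. An event coded to a general anaemia term would probably still be caught.

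**4. What one case is worth.** This is an illustration, not an estimate. Both documents equate 20–60% of subjects with 40–120 completers, so the implied base is 40/0.20 = 120/0.60 = 200. The allocation is not given. If six groups were equal, each would have 200/6 ≈ 33.

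- If the excluded case were the group's only anaemia, 1/33 = 3.0% (exact 95% CI 0.1 to 15.8%) would be reported as 0/33 = 0% (0 to 10.6%).
- For groups of 20 to 50, one case is 1/20 = 5.0% to 1/50 = 2.0%.
- The SAP's planned output is a normal-approximation interval for a difference. For 1/33 against 0/33, the standard error is √(0.0303 × 0.9697 / 33) = 0.0298. The interval is 3.0% ± 1.96 × 2.98%, or −2.8% to 8.9%. With the case left out, the estimate is 0.

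**The case against.** The strongest objection concerns consequence. A reader might infer that an excluded case would surface only as a preferred term in general tables, or would be lost. The SAP does not support that. Serious events and events leading to discontinuation are tabulated and listed. Because Protocol 6.1 gives blood dyscrasias as an example of an important medical event, a haemolytic or aplastic anaemia could well be reported as serious and so be listed individually. Haemoglobin is graded whatever the cause. The interim review includes serious events and haematology, the data monitoring committee sees unblinded safety data, and SAP 9.2.2 lets further events be tabulated on clinical advice. This part of the objection stands in full.

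A second objection is that the query's contents are not in the documents, so the exclusion rests on its title. This also stands, and the conclusion has to be conditional on it.

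Third, Protocol 2.2 names anemia first among three potential risks but does not say that the order is a ranking, and it mentions neither haemolysis nor aplasia. Nothing in the documents ties the excluded types to either drug, so the mismatch is no evidence of a missed drug effect.

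Fourth, the arithmetic presupposes a case, and any single event would move a group of 33 by the same amount. That is correct: it shows scale, not likelihood.

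Fifth, using a standing company query is a normal sponsor convention. That explains how the row may have arisen. It does not make the row's scope match its label or the protocol's term.

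**Conclusion.** The mismatch is real and its effect is limited. The protocol's AESI is anemia of any type. The SAP's only search for it carries a title that excludes two types, under an unrestricted label and without a stated reason. If the query matches its title, the Anemia AESI count is incomplete and mislabelled in every AESI output, but no case disappears from the report.

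The number of events affected cannot be estimated, since the documents give no incidence for these types. That there will be few is an assumption. The conclusion rests on two conditions: the query's content matches its title, and the event is coded to a specific haemolytic or aplastic term. The point is worth correcting because the correction is small and an AESI line should count what its label says.

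**What to change.** In SAP Appendix B, split the Anemia row:

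- Sub-row 1: the current company query, unchanged.
- Sub-row 2: preferred terms for haemolytic and aplastic anaemia.
- Total: a subject with either, counted once, reported as the Anemia AESI.

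Use the total in SAP 9.2.2, 9.2.6, 9.2.11 and 11.0 and in the AESI percentages and rates of Protocol 7.4. Appendix B already splits malignancy into component rows, so the layout is familiar.

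The cost is one row and a search on events that are coded anyway, with no new data collection. The downside is that the total will no longer equal the standard company query, which matters for comparison with other studies; sub-row 1 keeps that figure visible.

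If the query does contain these terms, a footnote saying so closes the point. If the narrower scope is intended, the SAP should say so and give the reason, relabel the row, and align it with the protocol term. This is an analysis definition and touches no dose or clinical rule.

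### The protocol's renal AESI includes increased serum creatinine, but no SAP Appendix B search names it, so creatinine-increase AEs may be missing from the AESI outputs

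*SAP*

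**What the plan says.** Protocol 6.1 lists the AESIs to be monitored. The renal entry has two components under one name: "Increased serum creatinine and renal dysfunction".

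SAP 9.2.6 hands identification over to an appendix: "The AESI categories will be identified by the following search criteria". Appendix B repeats the rule: "Adverse Events of Special Interest (AESI) will be identified using the following search criteria". Its only renal row is labelled Renal Dysfunction, with query type SMQ, scope narrow, and search "Acute Renal, Failure". No row in the table names creatinine.

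The AESI classification is then used in several places. SAP 9.2.2 includes AESIs in the overview and adds: "For AESIs, the point estimate and 95% CI (using normal approximation) will be provided for the treatment difference in AE percentages". SAP 9.2.11 plans a "Listing of Subjects with Treatment-Emergent AESIs". SAP 11.0 names AESIs among the key safety endpoints for the interim analysis. Protocol 7.4 promises AESI percentages and rates per 100 patient-years.

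**The concern.** The protocol promises to report a two-part renal category, and the SAP gives a search for only one part. Under Protocol 6.1 an abnormal laboratory finding can be an AE, so an investigator may report raised creatinine as an event with no clinical diagnosis of renal failure. Whether that event counts as an AESI depends wholly on whether an acute renal failure query happens to return the term.

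At stake is how faithful the AESI outputs are to the protocol's definition. A reader of a row headed Renal Dysfunction could take it as the protocol's renal AESI in full when its laboratory half may not be there. The same would apply to the between-group AESI difference and to the AESI content of the interim review.

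**Working it through.** No arithmetic tests this point. It is a question of whether two definitions match, so the check sets them side by side and traces what depends on them.

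**Step 1: match the components.**

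| Component in Protocol 6.1 | Search named in SAP Appendix B |
|---|---|
| Increased serum creatinine | None |
| Renal dysfunction | Narrow acute renal failure SMQ |

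No other Appendix B row is a renal or creatinine search. The stray comma in the query title may be a typing or text-extraction artefact, and nothing here rests on it.

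**Step 2: look for another route into the AESI category.** SAP 9.2.6 points only to Appendix B, and 9.2.2, 9.2.11 and 11.0 give no AESI definition of their own. Protocol 6.1, Table 3, requires a renal supplemental form for several triggers, one of them "Serum creatinine > 2.0 mg/dL". The SAP does not use that form to identify AESIs, so it does not close the gap.

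**Step 3: compare with a similar AESI.** CPK elevation is also a laboratory-type AESI. Appendix B gives it its own row, with a search on a single preferred term. The same device would serve for creatinine and was not used.

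**Step 4: list the outputs affected.**

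| Output | SAP section |
|---|---|
| AESI line in the overview | 9.2.2 |
| AESI treatment difference with 95% CI | 9.2.2 |
| AESI table by SOC and PT | 9.2.6 |
| AESI listing | 9.2.11 |
| Interim AESI summary | 11.0 |

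That is five outputs in four sections. The AESI percentages and rates promised in Protocol 7.4 rest on the same classification.

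**Step 5: list the outputs not affected.**

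- Every treatment-emergent AE is tabulated by SOC and PT (SAP 9.2.3), and by severity and relationship (9.2.7, 9.2.8).
- Serious events and those leading to discontinuation have their own tables and listings (9.2.5, 9.2.11).
- Blood chemistry is drawn at each scheduled visit of the extension (Protocol Appendix D).
- Creatinine is graded by NCI CTC (SAP 9.3), with Grade 1 starting just above baseline or above the upper limit of normal (Table C-1 footnote).
- Shift tables and PCS counts with listings follow (SAP 9.3).
- The interim includes mean change and PCS results for chemistry (SAP 11.0).

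**Step 6: bound the size.** If the narrow query returns no creatinine-increase terms, all such AEs are missing from the five outputs. If it returns them all, none are missing. The documents give no term list, so the range cannot be narrowed from them.

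**The case against.** The strongest reply is that no loss has been shown. Whether any event is missed depends on the content of a query that neither document reproduces, and a range from none to all says little. That stands as far as counts go. It does not answer the definitional point: the protocol names a component, and the SAP names no search for it.

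A second reply is that the safety information is captured better elsewhere. Creatinine measured at each visit and graded from small rises upward is a more sensitive detector of a mild renal effect than investigator-reported terms. This is right. A reader might infer that an early renal signal would go unseen; the SAP does not support that, given the laboratory outputs and the full SOC/PT tables. What those outputs do not provide is an AESI count, an AESI difference with its interval, or an AESI listing. SAP 9.2.2 also lets further AEs be tabulated on clinical or safety advice, but that is an option, not a commitment.

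A third reply concerns milder renal impairment. A reader might infer from the query's title and narrow scope that such events are dropped as well. The documents do not support going that far. The sponsor assigned this query to a row labelled Renal Dysfunction, and its terms are not given. Nor does Table 3 settle it: that table lists triggers for a supplemental form, and collecting data more widely than an AESI search is not a contradiction.

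Finally, the hepatic row might seem a second example of a laboratory component handled fully, since its label mentions transaminases. It too is a single narrow SMQ with no added laboratory term, and a label retrieves nothing. Only the CPK comparison carries weight.

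**Conclusion.** The mismatch is real and confined to AESI reporting. Increased serum creatinine is part of a protocol AESI, and the SAP, followed as written, names no search for it. Five AESI outputs in SAP 9.2.2, 9.2.6, 9.2.11 and 11.0 would omit any creatinine-increase AE that the acute renal failure query does not return. How many that is cannot be determined from the documents.

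The conclusion assumes that Appendix B is the complete AESI definition, which is how SAP 9.2.6 presents it, and that investigators may report raised creatinine as an AE, which Protocol 6.1 allows. It makes no assumption about the query's content. It does not extend to loss of the events from safety reporting as a whole, or to a finding that lesser renal impairment is missed. The point deserves correcting because the correction is small and the protocol made the commitment.

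**What to change.** Add a separate Appendix B row for increased serum creatinine, identified by an explicit preferred-term search in the way CPK elevation is. Keep the narrow acute renal failure SMQ as its own Renal Dysfunction row, so that laboratory-type events and renal failure are shown apart.

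Check the term list of that SMQ in the MedDRA version used, for two purposes. First, see whether it already returns creatinine-increase terms. If it does, state whether those events appear in both rows or are removed from the SMQ row; Appendix B already uses removal to separate malignancy from non-melanoma skin cancer. Count each subject once in any overall AESI line. Second, see whether renal impairment terms are covered, and record the answer. If the sponsor prefers the narrower definition, the alternative is to say so in the SAP with a reason.

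The change is best made before the unblinded interim is reviewed, since widening an AESI definition afterwards could look data-driven. If the interim has already been reviewed, date the change and give its rationale.

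The cost is one table row and a term-list check. The downside is that more mild events will count as AESIs, which the separate row keeps visible. If the existing query already returns these terms, the overall AESI count does not change and the row simply documents coverage.
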